6.5.1 RESCUE MEDICINE

Not applicable.

7 STUDY INTERVENTION DISCONTINUATION AND PARTICIPANT DISCONTINUATION/WITHDRAWAL

7.1 DISCONTINUATION OF STUDY INTERVENTION

Discontinuation from study intervention does not mean discontinuation from the study, and remaining study procedures should be completed as indicated by the study protocol. If a clinically significant finding is identified (including, but not limited to changes from baseline) after enrollment, the investigator or qualified designee will determine if any change in participant management is needed. Any new clinically relevant finding will be reported as an adverse event (AE).

The study agent will be discontinued if the patient is admitted to the hospital.

The data to be collected at the time of study intervention discontinuation will include the following:

• Interview that participant regard their concern for discontinuation and assess for side effects/safety concerns.

7.2 PARTICIPANT DISCONTINUATION/WITHDRAWAL FROM THE STUDY

Participants are free to withdraw from participation in the study at any time upon request. An investigator may discontinue or withdraw a participant from the study for the following reasons:

- Subject withdraws consent
- Subject voluntarily withdraws from treatment
- Subject is unable to tolerate continued study drug administration
- Significant study intervention non-compliance
- Subject experiences a Grade 3 or higher adverse event attributed to the study drug by the investigator
- Subject experiences a Grade 3 or higher clinically significant laboratory abnormality attributed to the study drug by the investigator
- Subject's clinical condition has worsened to be considered "severe" or "critical"
- If the participant meets an exclusion criterion (either newly developed or not previously recognized) that precludes further study participation.
- Subject becomes pregnant
- Subject becomes lost to follow-up

The reason for participant discontinuation or withdrawal from the study will be recorded on the Case Report Form (CRF).

Patients that discontinue/withdraw from the study will continue to be followed for a minimum of 21 days after randomization to assess outcomes/hospitalization rates as allowed.

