4.4 END OF STUDY DEFINITION

A participant is considered to have completed the study after they have completed a minimum of 7 days of treatment, noting patient will be permitted to discontinue treatment after having 3 days of resolution of fever, fatigure, and dyspnea and they has been followed up with 60 days of enrollment by way of completing the last online survey, exit interview and/or chart review.

The study is considered complete after the last enrolled participant has completed the study.

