8.3.4 TIME PERIOD AND FREQUENCY FOR EVENT ASSESSMENT AND FOLLOW-UP

The occurrence of an adverse event (AE) or serious adverse event (SAE) may come to the attention of study personnel by way of participant online survey results and interviews of a study participant presenting for medical care, or upon review by a study monitor.

All AEs including local and systemic reactions not meeting the criteria for SAEs will be captured on the appropriate case report form (CRF). Information to be collected includes event description, time of onset, clinician's assessment of severity, relationship to study product (assessed only by those with the training and authority to make a diagnosis), and time of resolution/stabilization of the event. All AEs occurring while on study must be documented appropriately regardless of relationship. All AEs will be followed to adequate resolution.

Any medical condition that is present at the time that the participant is screened will be considered as baseline and not reported as an AE. However, if the study participant's condition deteriorates at any time during the study, it will be recorded as an AE.

Changes in the severity of an AE will be documented to allow an assessment of the duration of the event at each level of severity to be performed. AEs characterized as intermittent require documentation of onset and duration of each episode.

Research clinicians will record all reportable events with start dates occurring any time after informed consent is obtained until 7 (for non-serious AEs) or 30 days (for SAEs) after the last day of study participation. At each study visit, the investigator will inquire about the occurrence of AE/SAEs since the last visit. Events will be followed for outcome information until resolution or stabilization.

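### Section 7.2 permits study withdrawal for treatment-only reasons that 7.1 says do not end participation, so recording of new adverse events can stop 39 days early, or 55 on a stricter reading

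*Combined protocol and SAP*

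**What the plan says.** Section 7.1 separates the two kinds of stopping: "Discontinuation from study intervention does not mean discontinuation from the study, and remaining study procedures should be completed".

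Section 7.2 concerns leaving the study. It opens with "An investigator may discontinue or withdraw a participant from the study for the following reasons". Besides withdrawal of consent and loss to follow-up, its list includes "Subject voluntarily withdraws from treatment", "Subject is unable to tolerate continued study drug administration", significant non-compliance with the intervention, and "Subject experiences a Grade 3 or higher adverse event attributed to the study drug by the investigator". Of those who leave it says "Patients that discontinue/withdraw from the study will continue to be followed for a minimum of 21 days after randomization to assess outcomes/hospitalization rates", qualified by the words as allowed. It does not mention the safety surveys.

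Section 8.3.4 starts the recording of new events at informed consent and continues it "until 7 (for non-serious AEs) or 30 days (for SAEs) after the last day of study participation". It does not say which day that is for a withdrawn participant. The same section has all adverse events followed until they resolve, and 8.3.6 follows serious ones until they are resolved, chronic or stable.

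The synopsis sets participation at 60 days. Section 4.1 schedules the PRO-CTCAE on days 1, 8, 15, 21, 30 and 60. Section 4.4 has a participant "considered to have completed the study after they have completed a minimum of 7 days of treatment", together with 60-day follow-up.

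**The concern.** The same event, such as stopping the capsules because of stomach upset, has two outcomes in the protocol. Under 7.1 the participant stays and completes the remaining procedures. Under 7.2 the investigator may take the participant out of the study. Follow-up is then assured only to day 21, and only for outcomes and hospitalization. Since 8.3.4 counts its closing dates from the end of participation, an early exit also brings forward the day on which new events stop being recorded.

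Evaluating safety is a stated aim (4.1). The trial takes no laboratory studies of its own, so events come to light mainly through surveys and interviews. Section 9.4.4 counts each adverse event at most once per participant and states no adjustment for unequal follow-up, so a shorter observation period can only lower the count. If length of observation depends on how the participant tolerated the agent, the truncation is informative. The pause in enrollment after 100 participants relies on 21-day data (8.3.1, 9.4.6), and that review could also be thinned if recording of non-serious events closes before day 21.

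**Working it through.** The plan states no figure on this point, so there is none to reproduce. The check is day arithmetic on the protocol's own windows, with all days on one scale.

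Inputs:
- Planned participation: 60 days (synopsis).
- Assured follow-up after withdrawal: 21 days from randomization, as a minimum (7.2).
- End of new-event recording: 7 days (non-serious) or 30 days (serious) after the last day of participation (8.3.4).
- PRO-CTCAE days: 1, 8, 15, 21, 30, 60 (4.1).

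Let L be the last day of participation. Non-serious recording ends on day L + 7 and serious recording on day L + 30. Compared with a participant followed to day 60, each window is shorter by 60 − L days.

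| L | Reading | Non-serious, L + 7 | Serious, L + 30 | Shortfall, 60 − L | PRO-CTCAE not assured |
|---|---|---|---|---|---|
| 60 | full follow-up | 67 | 90 | 0 | none |
| 21 | the floor in 7.2 | 28 | 51 | 39 | days 30, 60 |
| 15 | day of withdrawal | 22 | 45 | 45 | days 21, 30, 60 |
| 10 | day of withdrawal | 17 | 40 | 50 | days 15, 21, 30, 60 |
| 5 | day of withdrawal | 12 | 35 | 55 | days 8, 15, 21, 30, 60 |

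Three things follow:
- The 7.2 floor leaves 60 − 21 = 39 of 60 days (65%) unassured. Any L of 21 or less shortens both windows by at least 39 days.
- The non-serious window closes before day 21 when L + 7 < 21, that is, for L below 14. This happens only if L is read as the day of withdrawal.
- The serious window always passes day 21, because L + 30 is at least 31 for any L from day 1.

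The text does not settle which reading of L applies. That 7.2 keeps following these participants to day 21 favors L = 21. That it calls them withdrawn from the study favors the day of withdrawal.

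**The case against.** The strongest reply is that the day-21 sentence is not the safety rule. It is a minimum, and it concerns outcomes and hospitalization. Safety is governed by 8.3.4 and 8.3.6, which follow known events to resolution or stability and make no exception for withdrawn participants. The event that led to withdrawal is therefore followed without a day limit. This stands, and it limits the point to the detection of new events.

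Other parts of the reply also stand. Section 7.2 is permissive, so an investigator can keep the participant under 7.1. The floor applies to every reason for withdrawal, not only to toxicity. Section 7.1 requires an interview about side effects when the agent is stopped, and 5.5 has a retention provision for participants considering withdrawal because of GI effects. The 55-day shortfall and five surveys are the result of one reading and one example day; on the other reading they are 39 days and two surveys.

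A reader might infer that the comparison of arms is biased in favor of resveratrol, because section 2.3 names GI upset as its main risk. The documents do not support that step. They give no withdrawal rates by arm. Section 4.3 calls GI effects infrequent at doses of 1 g or less. The 7.2 list also includes worsening to severe or critical disease, which would fall more on placebo if resveratrol works. The forces oppose each other, and neither the size nor the direction of the net effect can be derived.

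What the reply does not remove is the contradiction. A permissive rule leaves the length of follow-up to case-by-case discretion, and following a known event to resolution does not detect a later, different one.

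**Conclusion.** Sections 7.1 and 7.2 conflict, and 8.3.4 turns the conflict into unequal detection of new events. For a participant withdrawn on a treatment-only ground, recording can end on days 28 and 51 (39 days early, with the day-30 and day-60 PRO-CTCAE not assured) or, for a day-5 withdrawal on the stricter reading, on days 12 and 35 (55 days early, with up to five surveys not assured). Full follow-up gives days 67 and 90. These figures assume that the investigator uses the discretion in 7.2 and that nothing beyond the assured minimum is done. How many participants this would affect cannot be derived from the documents.

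Two further readings go too far. A reader might infer that all safety follow-up stops at day 21 where toxicity occurs; the rules for events already reported rule that out. A reader might also infer from 4.4 that someone treated for fewer than 7 days drops out of the analysis. Section 9.3 defines only an intention-to-treat population (all randomized) and a safety population (at least one dose reported), so completer status removes nobody.

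The 21-day primary endpoint is still collected, as allowed, and the power calculation is unaffected. The matter merits correction because safety is a stated aim and the repair is simple.

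**What to change.** Reconcile 7.1, 7.2 and 8.3.4, without changing who stops treatment or when:

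1. State that stopping the agent, for whatever reason, is not in itself withdrawal from the study.
2. State that participants who stop the agent continue the scheduled PRO-CTCAE surveys, the exit interview and the chart review to day 60, unless they withdraw consent or are lost to follow-up.
3. In 8.3.4 keep the start at informed consent, so that events before randomization are not lost, and set the end of the recording window at the same fixed day for every randomized participant. Counting from planned day 60 gives day 67 for non-serious and day 90 for serious events, as for a participant followed to day 60 now.
4. For consistency, define study completion in 4.4 by day-60 follow-up rather than by days on treatment. This is minor, as no analysis population depends on it.

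The cost is amendment wording and a few more online surveys, through the existing system, for participants who have stopped the agent. They bear some extra burden and can still withdraw consent.

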7.3 LOST TO FOLLOW-UP

A participant will be considered lost to follow-up if we are unable to determine the patient's outcome

via participant survey, email correspondence, phone call to participant, phone call to secondary contact, and if information regarding their condition cannot be determined via the electronic medical record including after attempting to obtain records from surrounding hospital systems (Ohio State University and OhioHealth). Vital record search will also be used, if necessary, to determine outcomes in participants lost to follow up.

8 STUDY ASSESSMENTS AND PROCEDURES

8.1 EFFICACY ASSESSMENTS

Outcome Assessment and Other Key Variables. Hospitalizations will be determined based on query of subject and/or the subject's secondary contact. The subject's medical records will be requested from the admitting hospital (and discharging hospital, if separate) via a HIPAA authorization.

Additional outcomes will include daily reporting of fever to assess number of days with fever and assess severity of dyspnea and fatigue. Questionnaires to assess symptoms and adverse events will be used to monitor patients based on the PRO-CTCAE (see appendix 12.6) (National Cancer Institute, 2020).

Conditions that the CDC defines as being high risk for developing severe COVID-19, and pertinent medications will be recorded.

Adverse events will be recorded using PRO-CTCAE and CTCAE.

8.2 SAFETY AND OTHER ASSESSMENTS

Safety Monitoring. This study while only be initiated after approval by Mt Carmel Health System's Research Advisory Review Committee (RARC), Institutional Review Board (IRB), and the Food and Drug Administration (FDA).

An independent Data and Safety Monitoring Board (DSMB) will been convened to assess the progress of a clinical study, the safety data, and critical efficacy endpoints (if appropriate) and provide recommendations. The members of the DSMB serve in an individual capacity and provide their expertise and recommendations. The DSMB will review cumulative study data to evaluate safety, study conduct, and scientific validity and data integrity of the study. The charter for the DSMB was developed by the Trinity Health research department.

In addition to daily self-assessment via survey, participants will be provided with a consumer grade finger pulse oximeter. They will be instructed to (at minimum) record their resting pulse oximeter reading of pulse rate and oxygen saturation each evening. Patients will be instructed to seek medical attention for best resting oxygen saturation (SaO2) <94% on room air, or resting heart rate \geq 90 beats per minute. Patients will be cautioned faulty readings and techniques for accurate readings. Consumer grade pulse oximeters report an accuracy of +/- 2%.

8.3 ADVERSE EVENTS AND SERIOUS ADVERSE EVENTS

8.3.1 DEFINITION OF ADVERSE EVENTS (AE)

For this study, an adverse event is defined as "any untoward medical occurrence associated with the use of a drug in humans, whether or not considered drug related." [21 CFR 312.32(a)] At the dosing used in this study, the investigators do not anticipate a higher than minimal risk of adverse events which occur

due to the use of resveratrol. Data on adverse events will be collected for this study via the online questionnaires based on as selection of PRO-CTCAE questions as well as exit interviews graded according to the Common Terminology Criteria for Adverse Events (CTCAE) and assessed for their potential relationship to the study agent (see: https://evs.nci.nih.gov/ftp1/CTCAE/About.html).

Data safety monitoring will be conducted by an independent Data Safety Monitoring Board. The DSMB biostatistician will prepare reports for the principal investigator which summarizes the adverse events and serious adverse events, by group (labelled 'A' and 'B'), type of event and frequency. An initial planned interim safety analysis of the first 100 participants by the DSMB will occur after the first 21-day data is collected from the 100th participant. Enrollment of new subjects will be paused pending the results of DSMB review the first 100 participants. The study will resume enrollment upon DSMB approval. The monitoring Institutional Review Board (IRB) will receive all serious adverse event reports generated for this trial. Decisions regarding stopping the trial for safety reasons will be made after consultation with the IRB and/or DSMB.

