6.2.4 PREPARATION

Unmodified commercially available RV capsules and manufacturer prepared placebo capsules contained in manufacturer sealed bottles will be re-labelled with the study instructions. The bottles that have been prepared with study instruction will be turned over to an independent statistical consulting service (professors from Capital University department of Mathematics, Computer Science, and Physics) who will prepare the randomization table. Steps will be put in place to temporarily differentiate placebo vs RV bottles. Tamper-resistant serialized (sequentially numbered) stickers will be assigned to placebo or RV and affixed to the appropriate bottles. Bottles will be returned to the research team differentiated only by their unique serial number. The randomization table will be kept by OSU's consulting service and forwarded to the DSMB. The research team will only get access to the randomization list only after the completion of the study.

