8.3.2 DEFINITION OF SERIOUS ADVERSE EVENTS (SAE)

A serious adverse event is an adverse event that, in the opinion of the investigator or sponsor, results in: 1) death or is life-threatening (immediate risk of death); 2) hospitalization or prolongation of existing hospitalization; 3) persistent or significant incapacity or substantial disruption of the ability to conduct normal life functions (aka disability); or 4) congenital anomaly / birth defect.

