8.3.3.3 Expectedness

Research physicians will be responsible for determining whether an adverse event (AE) is expected or unexpected. An AE will be considered unexpected if the nature, severity, or frequency of the event is not consistent with the risk information previously described for the study intervention

Expected RV AE		
Diarrhea	Nausea	Gas/Bloating
Expected COVID AE		
Fever	Fatigue	Dry Cough
Loss of appetite	Body Aches	Shortness of breath
Mucus/phlegm	Sore Throat	Headache
Chills	Loss of smell/taste	Stuffy nose
Nausea or Vomiting	Diarrhea	Stroke
Conjunctivitis	Lower extremity numbness,	"COVID Toes"
	swelling, pain	
Arrhythmias	Heart Attacks	Cardiomyopathy
Pulmonary Embolism	Death	

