9.4 STATISTICAL ANALYSES

9.4.1 GENERAL APPROACH

Uncensored data will be summarized by percentages, means and standard deviations, or medians and ranges as appropriate for each variable's distribution. Data subject to censoring (e.g., hospitalization) will be summarized by Kaplan-Meier estimate.

Unless otherwise noted, all hypothesis tests will be two-sided and at the 5% significance level. Similarly, confidence intervals will be two-sided and at the 95% confidence level. Declarations of superiority will be declared if the corresponding hypothesis test is significant and the direction of the estimated treatment effect is favorable to resveratrol.

In addition to local hypothesis tests, we will use a multiple testing procedure to control the familywise Type I error at 5% for the primary and secondary endpoints together. The primary efficacy endpoint (hospitalization) will be tested at the 5% significance level; then, if the primary endpoint null hypothesis is rejected, the two secondary endpoints (ICU admission, invasive ventilation) will be tested via the Bonferroni-Holm procedure. No multiple testing adjustment will be made for exploratory or safety analyses.

Hospitalization, ICU admission, and invasive ventilation endpoints are composites that include death within 21 days of randomization.

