9.4.2 ANALYSIS OF THE PRIMARY EFFICACY ENDPOINT(S)

The primary efficacy endpoint is hospitalization for any cause within 21 days after randomization, as established by medical record review. Outcomes of subjects who withdraw consent or are otherwise lost to follow-up before 21 days will be considered missing. The intention to treat population for the hospitalization endpoint will be used for analysis. A logistic regression model will be fit with age, sex, race, ethnicity, risk group (see Sec 9.4.7), and randomized group as covariates, with the coefficient to randomized group as the primary estimand. Missing outcome data will be imputed using multiple imputation based on predictions from the logistic regression model of the outcome. Sensitivity analyses will include analyses in which patients lost to follow-up are assumed to not have been hospitalized, and tipping-point analyses systematically and comprehensively varying assumptions about missing outcomes on the treatment and placebo arms independently.

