9.4.6 PLANNED INTERIM ANALYSES

An independent DSMB will monitor safety data on a continual basis throughout the trial. One interim analysis will be carried out after the first 100 patients have completed the initial 21-day study period. After 100 patients have been randomized, enrollment will pause until all randomized patients have completed at least 21 days of follow-up to evaluate the primary endpoint and the interim analysis has been completed. The DSMB can recommend enrollment suspension or study termination for reasons of safety. Study enrollment will be suspended by the PI when (1) any subject experiences a Grade 3 or higher adverse event toxicity (defined in 8.3.3.1) that is probably, or definitely related to the study agent, or when (2) stopping is indicated by the statistical stopping rule defined below. An enrollment suspension under either scenario will trigger an ad hoc safety review by the DSMB. Following DSMB review and recommendation, the IRB and FDA will determine whether study enrollment will resume.

The interim and final analyses will use the Hwang-Shih-DeCani alpha spending function with parameter gamma = -4 (O'Brien-Fleming–like) for the upper (superiority) bound under the null hypothesis with total one-sided Type I error 2.5%, and for the lower (safety or futility) bound under the alternative hypothesis with total Type II error 20% (80% power). Under the assumption of a binding futility bound and a placebo arm hospitalization rate of 25%, the probability of declaring futility at the interim analysis is 3% if the resveratrol arm hospitalization rate is 10% (alternative hypothesis), 55% if the resveratrol arm hospitalization rate is 25% (null hypothesis), and 75% if the resveratrol arm hospitalization rate is 30%. The R package gsDesign will be used to determine stopping boundaries.

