10.1.6 SAFETY OVERSIGHT

Safety oversight will be under the direction of a Data and Safety Monitoring Board (DSMB) composed of individuals with the appropriate expertise, including [name] (statistics, epidemiology), [name] (pulmonologist), and [name] (ethics). Members of the DSMB should be independent from the study conduct and free of conflict of interest, or measures should be in place to minimize perceived conflict of interest. The DSMB will receive data to assess safety and efficacy data on each arm of the study after each quartile of participants have completed the study. The DMSB will operate under the rules of an approved charter that will be written and reviewed at the organizational meeting of the DSMB. At this time, each data element that the DSMB needs to assess will be clearly defined. The DSMB will provide its input to Principal Investigator

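### Section 8.3.1 sends the principal investigator adverse-event tables split by masked group, and those tables carry most of the primary-endpoint comparison

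*Combined protocol and SAP*

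**What the plan says.** - **The report.** Under 8.3.1 the DSMB biostatistician is to "prepare reports for the principal investigator which summarizes the adverse events and serious adverse events, by group (labelled 'A' and 'B", further broken down by event type and frequency. The named recipient is the principal investigator. No date or frequency is given for this report. The same paragraph places a DSMB safety review at 100 participants.
- **What counts as serious.** Section 8.3.2 lists death and "hospitalization or prolongation of existing hospitalization". Section 8.3.4 records worsening of a condition present at screening as an adverse event, so an admission for COVID-19 falls inside the definition.
- **The primary endpoint.** Section 9.4.2: "The primary efficacy endpoint is hospitalization for any cause within 21 days after randomization, as established by medical record review". Section 9.4.1 adds: "Hospitalization, ICU admission, and invasive ventilation endpoints are composites that include death within 21 days of randomization". The Section 3 table instead limits the endpoint to admissions for COVID-19 treatment, or death.
- **Who is meant to see comparative data.** Section 10.1.6: "The DSMB will receive data to assess safety and efficacy data on each arm of the study after each quartile of participants". Section 4.1 confines the randomization list to the third party and the DSMB while the trial runs. Section 6.2.4 says: "The research team will only get access to the randomization list only after the completion of the study".
- **The investigator's role.** Section 9.4.6: "Study enrollment will be suspended by the PI when (1) any subject experiences a Grade 3 or higher adverse event toxicity", if probably or definitely related to the study agent, or when the statistical stopping rule is met. Section 10.1.7 has the investigator or a designee review patient survey data at least weekly.

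**The concern.** An SAE table split by group is close to an endpoint table split by group when the endpoint is itself an SAE. Sections 4.1, 6.2.4 and 10.1.6 keep the allocation list from the research team and direct by-arm safety and efficacy data to the DSMB. Section 8.3.1 then sends a near-copy of the efficacy comparison to the investigator.

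The investigator suspends enrollment, and the investigator's team recruits patients, follows them up and judges whether adverse events are related to treatment. Knowing that one group is running well ahead of the other could affect how vigorously the team recruits, how it follows patients, and how it reads a borderline event.

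Neither suspension trigger in 9.4.6 needs the investigator to see group counts. The first is a single-case rule. The second is a boundary that a statistician can compute and report as met or not met.

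**Working it through.** **1. Overlap of the SAE table with the endpoint.**

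| Feature | SAE report (8.3.1, 8.3.2, 8.3.4, 9.4.4) | Primary endpoint (3, 9.4.1, 9.4.2) |
|---|---|---|
| Hospitalization | Any | Any cause (9.4.2) or for COVID-19 (3) |
| Death | Included | Included |
| Window | To 30 days after the last day of participation | 21 days from randomization |
| Population | Safety population for the safety analyses | All randomized |
| Source | Surveys, interviews, review | Medical record review |

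The two are not identical, but under either endpoint wording essentially every endpoint event is also an SAE. The reverse does not hold: the SAE table also contains later events and, under the Section 3 wording, admissions for other causes.

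**2. The plan's own rates.** Section 9.2 assumes 25% on placebo and 10% on resveratrol, 95 complete observations per arm and 80% power. As a check, with p̄ = 0.175:

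power = Φ{[√95 × 0.15 − 1.96 × √(2 × 0.175 × 0.825)] / √(0.25 × 0.75 + 0.10 × 0.90)} = Φ{(1.462 − 1.053) / 0.527} = 0.781.

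Exactly 80% needs a resveratrol rate of 9.7%, which rounds to the stated 10%. The plan's figure reproduces, so its rates are used below.

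**3. What a masked table would show.** Let X ~ Binomial(n, 0.25) be placebo hospitalizations and Y ~ Binomial(n, 0.10) resveratrol hospitalizations, independent; the probabilities are exact sums. Equal arms are assumed. The case n = 50 per arm corresponds to the 100-participant review. The case n = 25 per arm assumes that a report follows the first quartile look in 10.1.6.

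| n per arm | Expected X v Y | P(X > Y) | P(X = Y) | P(X < Y) | P(X − Y ≥ 5) |
|---|---|---|---|---|---|
| 50 | 12.5 v 5.0 | 0.971 | 0.014 | 0.015 | 0.790 |
| 25 | 6.25 v 2.5 | 0.894 | 0.055 | 0.051 | 0.385 |

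The A/B labels hide which group is which. They do not hide the size of the gap.

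**4. The same table if there is no effect (25% in both arms).** The labels differ by at least 5 hospitalizations, in either direction, with probability 0.30 at n = 50 and 0.14 at n = 25. Under 25% v 10% the corresponding two-sided figures are 0.79 and 0.39.

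**5. Could the labels be guessed?** The same report lists adverse events by type, and GI upset is the known effect of resveratrol. The documents give no rates, so the rates below are assumptions, at 50 per arm.

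| Assumed GI rate, resveratrol v placebo | Resveratrol label higher | Tie | Placebo label higher |
|---|---|---|---|
| 20% v 15% | 0.702 | 0.085 | 0.214 |
| 35% v 30% | 0.666 | 0.074 | 0.260 |
| 25% v 15% | 0.872 | 0.045 | 0.082 |
| 30% v 15% | 0.956 | 0.018 | 0.026 |

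A small difference makes the guess unreliable; a clear one makes it usually right. Two passages point toward a small difference. Section 8.3.3.3 lists diarrhea for both resveratrol and COVID-19, with nausea under resveratrol and "Nausea or Vomiting" under COVID-19. Section 4.3 calls GI effects infrequent at doses of 1 g or less.

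**The case against.** **Timing and distribution are not fully visible.** Section 8.3.1 gives no schedule, 10.1.6 sends by-arm data to the DSMB, and the DSMB charter is not in the documents. This stands as a limit, which is why the conclusion covers only reports issued during the trial. The sentence does sit in a monitoring paragraph that ends with stopping decisions, so that is the natural reading. An unseen charter does not cancel the recipient named in the protocol.

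**Endpoint SAEs may be handled separately.** Section 8.3.6 recognises that some study endpoints are SAEs. It says only that they are reported according to the protocol, and does not remove them from the group tables.

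**A gap between masked labels is weak evidence.** At 50 per arm a gap of 5 or more arises by chance with probability 0.30 when there is no effect. Its direction is hidden, and 2.3.2 names a possible harm mechanism, so the investigator cannot presume which label is active. This is right as far as it goes: the table misleads as well as informs. It does not make the disclosure harmless, since a chance gap can influence conduct as easily as a real one.

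**The route to bias is narrow.** The endpoint comes from medical records, packets are numbered in sequence, the sample is capped at 200, and the IRB and FDA decide whether enrollment resumes after a suspension. All of this stands, and no bias is shown.

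**The investigator has reporting duties** (8.3.5, 8.3.6). These can be met from single-case reports and DSMB recommendations, but the revised text should not leave the by-group safety assessment without an owner.

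**Conclusion.** The concern holds. As written, the plan gives the investigator a by-group count that contains nearly all primary-endpoint events, outside the restriction set by 4.1, 6.2.4 and 10.1.6. The step 3 figures rest on the plan's 25% v 10% rates, equal arms and reports issued while the trial is running; the 25-per-arm case also assumes a report after the first quartile.

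The claim has limits. Group totals reveal no individual patient's allocation, the labels stay masked, and inferring them would need a clear GI difference that the documents neither give nor exclude. This is an avoidable risk to trial conduct, not evidence of bias. It should be fixed because the text is clear and the DSMB loses nothing by the change.

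**What to change.** - **Section 8.3.1:** send tables split by group, whether labelled A/B or named, only to the DSMB and its statistician. Give the investigator pooled adverse-event and SAE counts, plus single-case reports without group labels. State when each report is issued.
- **Section 9.4.6, second trigger:** the DSMB statistician evaluates the stopping boundary and tells the investigator only whether to continue or suspend.
- **DSMB charter:** match both changes, and record that the DSMB makes the by-group safety assessment, so that the investigator's duties under 8.3.5 and 8.3.6 rest on single cases and DSMB recommendations.

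The cost is about one sentence in each of the two sections, matching charter text, and one additional pooled report for the statistician to prepare. The investigator loses the by-group view. The DSMB keeps it, so its safety review is unchanged.
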